6.2 FIDELITY

6.2.1 INTERVENTIONIST TRAINING AND TRACKING

Training and Tracking:

The PI will train research staff on data collection using REDCap. All training will be documented on a training log. This will include dates and times of the trainings, and printed names and signatures of the trainees and PI.

6.3 MEASURES TO MINIMIZE BIAS: RANDOMIZATION AND BLINDING

Randomization:

Randomization will be performed with a 1:1 allocation ratio. Balanced treatment assignments will be achieved using permuted block randomization with random block sizes. The study biostatistician will generate a randomization schedule using the SURVEYSELECT procedure in SAS. Assignments will not be seen by other study personnel in advance and will not be changed after randomization.

Blinding:

Study personnel will be unblinded to the randomization, as it will be clear the number of participants who have a 12-week delay and those who do not. In addition, it will be clear to participants which treatment group they are in and it will be impossible to blind them from this information.

6.4 STUDY INTERVENTION/EXPERIMENTAL MANIPULATION ADHERENCE

Participants will be asked to adhere to study visits and to complete study assessments. Participants will remain active unless withdrawn from the study (see **Section 7**). We will track participants' adherence to study visits, as well as completion of the assessments. These will be documented in the relevant eCRF.

6.5 CONCOMITANT THERAPY

Participants may use over-the-counter medications, dietary supplements, and prescribed medications. Medications will be assessed at each study visit and documented in the relevant eCRF.

6.5.1 RESCUE THERAPY

N/A

7 STUDY INTERVENTION/EXPERIMENTAL MANIPULATION DISCONTINUATION AND PARTICIPANT DISCONTINUATION/WITHDRAWAL

7.1 DISCONTINUATION OF STUDY INTERVENTION/EXPERIMENTAL MANIPULATION

When a participant who signed the consent form chooses to discontinue participation in the study after beginning the study intervention, or if the principal investigators (PIs) and co-investigators determine that a participant should discontinue participation, they will be withdrawn from the study. A withdrawal will either be defined as 'Patient Withdrawal' or 'PI Withdrawal'. The participant will be asked to complete an early withdrawal visit within 14 days from the date the intervention was discontinued. The purpose of the visit will be to obtain study outcome data and to record any AEs or serious adverse events (SAEs) that may have occurred after the discontinuation of the intervention. Research staff will attempt to call the participant up to 3 times to set up an in person visit.

The data that will be collected at the time of study withdrawal will include the following:

- The reason(s) for discontinuation of the study intervention

The data that will be collected during the early withdrawal visit will include the following:

- Blood sample
- Strength and cardiovascular testing (if medically able)
- Medication review
- AEs or SAEs that occurred since the time of withdrawal
- SCI-QOL via e-mail survey

7.2 PARTICIPANT DISCONTINUATION/WITHDRAWAL FROM THE STUDY

Participants are free to withdraw from participation in the study at any time upon request.

An investigator may discontinue a participant from the study for the following reasons:

1. Participant has not completed a intervention treatment session for > 10 days, unless a participant has an illness, such as COVID-19. In this case, additional time may be allowed, as determined by the investigator.
2. Significant study intervention non-compliance during exercise sessions
3. Lost-to-follow up; unable to contact subject (see **Section 7.3, Lost to Follow-Up**)
4. Any event or medical condition or situation occurs such that continued collection of follow-up study data would not be in the best interest of the participant or might require an additional treatment that would confound the interpretation of the study
5. The participant meets an exclusion criterion (either newly developed or not previously recognized) that precludes further study participation

The reason for participant discontinuation or withdrawal from the study will be recorded on the relevant eCRF. Subjects who sign the informed consent form and are randomized but do not receive the study intervention may be replaced. Subjects who sign the informed consent form, and are randomized and

receive the study intervention, and subsequently withdraw, or are discontinued from the study, will not be replaced.

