 - Take the patient to the rehabilitation gym for strength and cardiovascular testing (described in detail below)
- Patient will be asked to complete the Spinal Cord Injury-Quality of Life (SCI-QOL) short forms via e-mail survey within 3 days (approximately 30 minutes).

4. Pre-treatment Visit 2 (Group 2 only)

- Duration: Approximately 1 hour in person
- Research staff will:
 - Complete the Medication review in REDCap.
 - Have the laboratory staff obtain a blood sample from the patient.
 - Take the patient to the rehabilitation gym for strength and cardiovascular testing.
- Patient will be asked to complete the SCI-QOL short forms via e-mail survey within 3 days (approximately 30 minutes).

5. Study Intervention (Groups 1 & 2)

- Duration: Each visit approximately 1 hour
- The exercise physiologists will:
 - Complete the Adverse Events (AE) Reporting, Medication Review, and Treatment Adherence in the relevant eCRFs in REDCap.
 - Provide exercise instruction as described in more detail below.

6. Post-treatment Visit 1 (Groups 1 & 2)

- Duration: Approximately 1 hour in person
- Research staff will:
 - Complete the Medication review in REDCap.
 - Have the laboratory staff obtain a blood sample from the patient.

- Take the patient to the rehabilitation gym for strength and cardiovascular testing.
- Patient will be asked to complete the SCI-QOL short forms via e-mail survey within 3 days (approximately 30 minutes).

7. Post-treatment Visit 2 (Groups 1 & 2)

- Duration: Approximately 1 hour in person
- Research staff will:
 - Complete the Medication review in REDCap.
 - Have the laboratory staff obtain a blood sample from the patient.
 - Take the patient to the rehabilitation gym for strength and cardiovascular testing.
- Patient will be asked to complete the SCI-QOL short forms via e-mail survey within 3 days (approximately 30 minutes).

8. Early Withdrawal Visit (For patients who begin the intervention and then withdraw from the study.)

- Duration: Approximately 1 hour in person
- Research staff will:
 - Complete the Medication review in REDCap.
 - Have the laboratory staff obtain a blood sample from the patient.
 - Take the patient to the rehabilitation gym for strength and cardiovascular testing (if medically able).
- Patient will be asked to complete the SCI-QOL short forms via e-mail survey within 3 days (approximately 30 minutes).

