2 INTRODUCTION

2.1 BACKGROUND & STUDY RATIONALE

Two of the most common causes of death in people living with spinal cord injury (SCI), cardiovascular and respiratory disease, have been linked to chronic low-grade inflammation.¹ Inflammation has also been linked to obesity, pulmonary issues, diabetes, and poor wound healing.² Although some levels of inflammation in the body can be considered “good” (e.g. inflammation occurs during injury repair), chronic inflammation can have negative consequences. Fortunately, chronic inflammation after a SCI could likely be reduced through modifiable risk factors, as described below.

Higher levels of inflammatory biomarkers are observed in SCI when compared to healthy individuals. Biomarkers are measurable substances from the body (e.g. blood serum). C-reactive protein, which is a marker of both inflammation and cardiovascular disease, was reported to be higher in adults with chronic SCI.³ Proinflammatory cytokines (signaling molecules that promote inflammation) interleukin 6 (IL-6) and tumor necrosis factor alpha (TNF- α), and the IL-1 receptor agonist (IL-1RA) (produced in response to infection or inflammation) are also increased.⁴ Finally, Antiganglioside (anti-GM₁) immunoglobulin (IgG), which are antibodies that are typically also present in autoimmune diseases (e.g. Guillain–Barré syndrome), have also been shown to be elevated.⁴ Not only are these inflammatory biomarkers elevated

in individuals with SCI, they are even more elevated in those with medical complications (e.g. urinary tract infection, pressure ulcers).⁴

A well-known method to reduce inflammation is through exercise; however, due to limitations in mobility, individuals with SCI are among the most sedentary and inactive in the world.⁵ Muscle atrophy, damaged muscle innervation, and reduced muscle activation create barriers for individuals with SCI to exercise. In addition, exercise conditioning in persons with SCI is complicated, because its benefits can be potentially counterbalanced by both ineffective exercise activities and the consequences of imprudent exercise, lending to further injury and accelerated musculoskeletal decline. Individuals with SCI also frequently encounter challenges and barriers when navigating a typical gym space. Therefore, individuals with SCI may be limited in their ability to achieve anti-inflammatory benefits through exercise.

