4.2 SCIENTIFIC RATIONALE FOR STUDY DESIGN

Justification for an unblinded study: Because it will be clear to both study personnel and participants who will have a delayed start and who will start immediately, neither will be blinded in this study. This will be reported as a limitation of the study.

Justification for an uncontrolled study with no control group: N/A

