9.4 STATISTICAL ANALYSES

9.4.1 GENERAL APPROACH

Discrete variables will be summarized using frequencies and percentages, while continuous variables will be summarized by means and standard deviations. If the continuous variables are found to be skewed, we will instead report medians and interquartile ranges. Statistical significance will be determined using p-values less than 0.05 and 95% confidence intervals, unless otherwise indicated. All inferential tests will be two-sided. For descriptive statistics (means, SDs, proportions) where no inferential statistics were conducted, we will refrain from making confirmative statements. All covariates will be pre-specified in the sections below. Any additional analyses will be described as post-hoc and exploratory.

Distribution of the outcome variables will be assessed prior to conduct of our analyses to determine if the planned tests are appropriate and to identify outliers. If variables are found to be non-normally distributed and/or outliers are present we will explore the use of log-transformations or non-parametric tests such as the Kruskal-Wallis test.

Patients who do not complete all assessments required for a given analysis will be excluded from the model/test and described separately. If missingness > 10% within the full analytic dataset, a comparison of participants with and without missing values will be performed and used to inform possible next steps (imputation, feasibility assessment of program, etc.). Reports of injury, illness, and life events occurring during the data collection period will be summarized and compared between arms. These summaries will be used to inform possible sensitivity analysis as described in section 9.4.10. All analysis will be performed in SAS 9.4 using two-sided alphas of 0.05 to determine significance.

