9.4.2 ANALYSIS OF THE PRIMARY ENDPOINT(S)

The primary outcome, change in inflammatory biomarker (CRP, IL-6, TNF- α), will be measured using a series of blood draws as described in **Section 6.1**. For our primary analysis, we are interested in the change over the course of the first 3 months, during which group 1 completes the exercise program and group 2 acts as a control. The change in inflammatory biomarker will be calculated by measuring the difference between the first and second measurement for each participant. We will then present the mean change by group with corresponding standard deviations. Analysis of covariance (ANCOVA) will be used to compare the change in each of the 3 inflammatory biomarkers between groups: An unadjusted model will account for a participant's baseline biomarker measurement while an adjusted model will include the set of covariates identified in **Section 9.4.6**. If these analyses identify a significant difference in change of inflammatory biomarkers associated with participation in the exercise program, next steps will assess if this change is still present three months after completing the exercise program. Using data from both groups in aggregate, paired t-tests will be used to compare the inflammatory marker level directly after participation in the exercise program and inflammatory marker levels three months afterward.

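### Section 7.2 item 4 allows discontinuation from the study over a confounding treatment; in the primary 12 weeks this can act far more readily in Group 1, and the planned ANCOVA would then leave those people out

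*Combined protocol and SAP*

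**What the plan says.** **The rule.** Section 7.2 opens with "An investigator may discontinue a participant from the study for the following reasons". Item 4 has two limbs. One is that continued data collection would not be in the participant's best interest. The other is that the event "might require an additional treatment that would confound the interpretation of the study". No list of such treatments is given. Section 6.5 states: "Participants may use over-the-counter medications, dietary supplements, and prescribed medications".

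**Who decides.** Section 4.2 says of study personnel and participants that "neither will be blinded in this study".

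**The primary window.** Section 9.4.2 compares change over the first 3 months, "during which group 1 completes the exercise program and group 2 acts as a control". In Section 1.3, Group 1 has Visits 3 to 38 in that window, and at each the exercise physiologists "Complete the Adverse Events (AE) Reporting, Medication Review, and Treatment Adherence in the relevant eCRFs in REDCap". Group 2 goes from Visit 2 to Visit 3 with nothing scheduled between. Under 8.3.4, adverse event recording starts only after the first exercise session, so Group 2's wait falls outside it.

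**What follows discontinuation.** Under 7.1 a person the investigators decide should discontinue is withdrawn from the study. Those who began exercise are asked to an early withdrawal visit, with a blood sample, within 14 days of stopping.

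**Analysis.** Section 9.3 says all analyses are intention-to-treat. Section 9.4.1 says "Patients who do not complete all assessments required for a given analysis will be excluded from the model/test and described separately". Section 9.4.10 analyses separately those who choose to withdraw early and attend the early withdrawal visit.

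**The concern.** The second limb of item 4 concerns interpretation of the data, and it is applied after randomisation by people who know the arm. Whether it can act before the second primary draw depends on an illness coming to light before then. Group 1 is asked at every session. Group 2's first scheduled medication review after baseline is at the same visit as its second primary draw.

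The reason for removal is also tied to the outcome. Section 2.1 says of the inflammatory markers that "they are even more elevated in those with medical complications (e.g. urinary tract infection, pressure ulcers"), and 8.1 expects illness to affect them. If people with raised markers are lost mainly from Group 1 and 9.4.1 then drops them, the comparison can show a reduction that exercise did not cause. With 10 per arm, one or two removals are enough to matter.

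**Working it through.** **1. The plan's own figure.** Section 9.2 gives 80% power for a 1.3 SD difference with 10 per arm at a 5% level. For a two-sided t-test with 18 df, the noncentrality is 1.3/√(1/10 + 1/10) = 2.91 and power is 78.5%. Power of 80% is reached at 1.325 SD, which rounds to 1.3. The figure reproduces.

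**2. Can the rule act before the second draw?**

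| | Group 1 | Group 2 |
|---|---|---|
| Scheduled contacts between the two primary draws | 36 (Visits 3 to 38) | 0 |
| Medication review between draws | Every session | None |
| Adverse event recording between draws | From the first session | Not started |
| Early withdrawal blood sample | Yes, within 14 days of stopping | No, exercise not begun |
| Replacement if the person leaves (7.2) | Not once exercise has begun | Allowed |

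The one illness question common to both arms is the 7-day recall at the pre- and post-treatment visits (8.1).

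**3. Does a removed person reach the primary ANCOVA?** The outcome is the second measurement minus the first. A person withdrawn in week 5, say, has no week-12 draw. No text makes the early withdrawal sample the second measurement, so 9.4.1 excludes the person despite 9.3.

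**4. Size. All inputs here are assumptions; none is in the documents.** Let q be the share of people with a treated complication that still raises the week-12 marker (10% to 30%), s the rise (1 to 2 SD), and r the share of such Group 1 people removed (50% or 100%). Nobody is removed from Group 2, and exercise has no effect.

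Expected Group 1 minus Group 2 difference = q(1 − r)s/(1 − qr) − qs.

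- r = 1: the difference is −qs, from −0.1 × 1 = −0.10 SD to −0.3 × 2 = −0.60 SD. At q = 20% and s = 2 it is −0.40 SD.
- r = 0.5, q = 10%, s = 1: 0.05/0.95 − 0.10 = −0.05 SD.
- r = 0.5, q = 30%, s = 2: 0.30/0.85 − 0.60 = −0.25 SD.

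Simulated ANCOVA of change on group and baseline (10 per arm, correlation 0.5, 8,000 runs per scenario):

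| Group 1 cases removed | Bias towards exercise | Chance of a falsely significant benefit |
|---|---|---|
| None | 0 | about 2.5% |
| Half | 0.05 to 0.25 SD | about 3% to 6% |
| All | 0.1 to 0.6 SD | about 4% to 13% |

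At q = 20%, s = 2 and all removed, the chance is 8.8%. Against the 1.3 SD design effect, the bias is 4% to 19% with half removed (0.05/1.3 and 0.25/1.3) and 8% to 46% with all removed (0.1/1.3 and 0.6/1.3).

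**5. When the bias vanishes.** If affected people are kept in both arms, or removed equally from both, the formula gives 0 and the two-sided error stays at about 5%. The bias therefore needs both unequal removal and the complete-case exclusion.

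**6. Power.** Losing 1, 2 or 3 people from Group 1 lowers power at 1.3 SD from 78.5% to 76.0%, 73.0% or 69.4%.

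**The case against.** A reader might infer that ill people do leave Group 1. The documents do not show this. Item 4 says investigators may act and applies to both arms; a Group 2 participant could be removed after reporting an illness. Item 1 allows extra time for illness. The only withdrawals on record (10.4) came before the intervention, with no arm given. This stands: the point is what the rules allow.

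The early withdrawal visit is meant to obtain outcome data, and 9.3 promises intention-to-treat. If that sample, taken near the illness, served as the second measurement, the bias would shrink or could reverse. But the plan does not say so, and the sample is timed to stopping exercise, not to week 12.

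One might also say that 6.5 contradicts item 4. It does not strictly: allowing medication does not promise continued participation. The two are unreconciled.

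Direction is not certain. A treatment that lowers the markers and is kept in Group 2 would work against exercise, and an illness that resolves before week 12 would leave no bias. With half removed, the two-sided error is only 4.8% to 6.9% against 5%.

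Finally, items 1, 2 and 5 can also remove ill people, and items 1 and 2 concern exercise sessions, so in this window they reach only Group 1. Changing item 4 alone would not close the route. This stands, and it shapes the fix.

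**Conclusion.** The plan allows outcome-related loss that is much more likely in Group 1, and its complete-case rule would carry that loss into the primary ANCOVA in spite of the intention-to-treat statement. The bias would probably favour exercise. Its size is modest if about half of the affected Group 1 participants are removed, and material only if nearly all are. These sizes rest on an assumed complication rate, marker rise and removal share, and on no Group 2 removals. It would go too far to conclude that the trial's result is biased, or that the problem is independent of missing-data handling: if the week-12 value is collected and analysed for everyone, the bias in this illustration is zero. The change is worth making because it is small and the trial has only 10 analysed participants planned per arm.

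**What to change.** - **Reconcile** 7.2 item 4 with 6.5, 7.1 and 9.3, so that a concern about confounded interpretation does not by itself end outcome collection. No change is proposed to when exercise stops or to the participant-interest ground.
- **Collect.** For anyone discontinued for any 7.2 reason who still consents, and where further data collection is not against their interest, seek the week-12 blood draw on the same schedule in both arms.
- **Analyse.** Include that draw as randomised in the primary ANCOVA, and state in 9.4.2 that the early withdrawal sample does not replace it there.
- **Sensitivity.** In 9.4.10, handle confounding treatments with one definition and the same 12-week window in both arms.
- **Report** removals by arm and reason.

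Cost: a few sentences in 7.1, 7.2, 9.4.2 and 9.4.10, one week-12 draw for the few people discontinued, and some extra noise from treated illness in the main analysis.

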7.3 LOST TO FOLLOW-UP

A participant will be considered lost to follow-up if he or she fails to attend any scheduled study visit and study staff are unable to contact the participant after at least 5 attempts, while maintaining the 10 day maximum between visits.

The following actions must be taken if a participant fails to attend any required study visit:

- Study staff will attempt to contact the participant, reschedule the missed visit, counsel the participant on the importance of maintaining the assigned visit schedule and ascertain if the participant wishes to and/or should continue in the study.
- Before a participant is deemed lost to follow-up, the investigator or designee will make every effort to regain contact with the participant (where possible, telephone calls or e-mail – if no answer leave a voicemail on the first and last attempt). These contact attempts will be documented.
- Should the participant continue to be unreachable, he or she will be considered to have withdrawn from the study with a primary reason of lost to follow-up.

8 STUDY ASSESSMENTS AND PROCEDURES

8.1 ENDPOINT AND OTHER NON-SAFETY ASSESSMENTS

Demographics: Demographic information will be collected, including: gender, age, race, ethnicity, language, height, zipcode, weight, marital status, employment status, medical history, and medications.

Injury, Illness, & Life Events: At all pre- and post-treatment visits, patients will be asked over the last 7 days whether they have had any injuries, illnesses, or major life events to report. This information will be tracked as it may likely impact inflammatory biomarkers.

Treatment Adherence: The participant's treatment adherence will be measured to determine tolerability of the intervention. We will record the number of attended sessions. We will also record participants' ability to complete the entire session.

Quality of Life: Participants will be asked to complete the SCI-QOL short forms, which include questions regarding quality of life, such as mobility, self-care, pain, and independence.

